For the DBL in December 2021 and final DBL, the following analysis populations are defined for efficacy and health outcome analyses.

Randomized Downtitration Withdrawal Substudy Population: All patients (including open-label patients) who are rerandomized at Week 52, enter the substudy, and receive at least 1 dose of the IP in Period 2.

Re-Treatment Substudy Population: A subset of Randomized Downtitration Withdrawal Substudy Population who experience IGA ≥ 3 at any time in Period 2 and receive at least 1 dose of retreatment of the original dose.

Period 2 Nonsubstudy Population: All patients randomized at Week 0 of main Study JAHN (excluding open-label patients) who are not eligible to enter the substudy at Week 52 and receive at least 1 dose of the IP in Period 2.

Open-Label Period 2 Nonsubstudy Population: All patients enrolled in the open-label addendum who are not eligible to enter the substudy at Week 52 and receive at least 1 dose of the IP in Period 2.

Long-Term Baricitinib 4 mg Population: Patients initially randomized to baricitinib 4 mg in the originating studies and remain on 4-mg up to Week 52 of Study JAHN. At Week 52 of Study JAHN, patients also need to continue 4-mg and receive at least one dose in Period 2 regardless of eligibility of entering sub-study.

Safety population: For the purpose of Study JAHN alone, the safety population is defined as all patients who received at least 1 dose of IP in Study JAHN and who did not discontinue from the study for the reason ‘Lost to Follow-up’ at the first postbaseline visit in Study JAHN. For the safety analysis of Treatment Period 2, patients with at least 1 dose of IP in Treatment Period 2 will be included in the safety analysis of Treatment Period 2.

Safety analyses will be performed using the safety population and will be analyzed according to the following treatment groups (or cohorts) defined in [Table JAHN.6.1](#). Patients will be analyzed according to the dosing regimen to which they were assigned.

Table JAHN.6.1. Safety Population Treatment Groups

Treatment Groups for Treatment Period 1 (Week 0-52)	Definition
PBO	Placebo at entry to Study JAHN followed to end of Treatment Period 1 or censored at treatment change
BARI 1 mg	BARI 1 mg followed to end of Treatment Period 1 or censored at dose or treatment change
PBO/BARI 1 mg to BARI 2 mg	PBO/BARI 1 mg switching to BARI 2 mg at entry to Study JAHN followed to end of Treatment Period 1 or censored at dose or treatment change

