BARI 2 mg	BARI 2 mg followed to end of Treatment Period 1 or censored at dose or treatment change
PBO/BARI 1 mg/BARI 2 mg to BARI 4 mg	PBO/BARI 1 mg/BARI 2 mg switching to BARI 4 mg at entry to Study JAHN followed to end of Treatment Period 1 or censored at dose or treatment change
BARI 4 mg	BARI 4 mg followed to end of Treatment Period 1 or censored at dose or treatment change
Pooled BARI	BARI 1 mg/BARI 2 mg/BARI 4 mg at entry to Study JAHN followed to end of Treatment Period 1 or censored at dose or treatment change
Treatment Groups for Treatment Period 2 (Week 52-200)	Definition
BARI 2 mg to PBO	Randomized to PBO in Treatment Period 2 (previously treated with BARI 2 mg) followed to end of study or censored at retreatment with BARI 2 mg

Treatment Groups for Treatment Period 2 (Week 52-200)	Definition
BARI 2 mg to BARI 1 mg	Randomized to BARI 1 mg in Treatment Period 2 (previously treated with BARI 2 mg) followed to end of study or censored at retreatment with BARI 2 mg
BARI 2 mg to BARI 2 mg	Randomized to stay on BARI 2 mg in Treatment Period 2 followed to end of study
BARI 4 mg to PBO	Randomized to PBO in Treatment Period 2 (previously treated with BARI 4 mg) followed to end of study or censored at retreatment with BARI 4 mg
BARI 4 mg to BARI 2 mg	Randomized to BARI 2 mg in Treatment Period 2 (previously treated with BARI 4 mg) followed to end of study or censored at retreatment with BARI 4 mg
BARI 4 mg to BARI 4 mg	Randomized to stay on BARI 4 mg in Treatment Period 2 followed to end of study
BARI 2 mg	Not part of the substudy, stayed on BARI 2 mg in Treatment Period 2 followed to end of study (this treatment group includes the open-label BARI 2 mg addendum patients)
BARI 4 mg	Not part of substudy, stayed on BARI 4 mg in Treatment Period 2 followed to end of study
Treatment Group for Treatment Periods 1 and 2 (Week 0-104) (for Box Plots Only)	Definition
PBO	Placebo at entry to Study JAHN followed to end of study or censored at treatment change
BARI 1 mg	BARI 1 mg followed to end of study or censored at dose or treatment change
BARI 2 mg to PBO	BARI 2 mg in Treatment Period 1, rerandomized to PBO in Treatment Period 2 followed to end of study or censored at retreatment with BARI 2 mg
BARI 2 mg to BARI 1 mg	BARI 2-mg in Treatment Period 1, rerandomized to BARI 1 mg in Treatment Period 2 followed to end of study or censored at retreatment with BARI 2 mg

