BARI 2 mg to BARI 2 mg	BARI 2 mg in Treatment Period 1, rerandomized to stay on BARI 2 mg in Treatment Period 2 followed to end of study
BARI 4 mg to PBO	BARI 4 mg in Treatment Period 1, rerandomized to PBO in Treatment Period 2 followed to end of study or censored at retreatment with BARI 4 mg
BARI 4 mg to BARI 2 mg	BARI 4 mg in Treatment Period 1, rerandomized to BARI 2 mg in Treatment Period 2 followed to end of study or censored at retreatment with BARI 4 mg
BARI 4 mg to BARI 4 mg	BARI 4 mg in Treatment Period 1, rerandomized to stay on BARI 4 mg in Treatment Period 2 followed to end of study
BARI 2 mg	BARI 2 mg in Treatment Period 1, did not enter the substudy and stayed on BARI 2 mg in Treatment Period 2 followed to end of study (this treatment group includes the open label BARI 2 mg addendum patients)
BARI 4 mg	BARI 4 mg in Treatment Period 1, did not enter the substudy and stayed on BARI 4mg in Treatment Period 2 followed to end of study

Abbreviations: BARI = baricitinib; PBO = placebo.

An all-baricitinib exposure, defined as patients valid for the safety population with at least 1 dose of baricitinib anytime during Study JAHN, will be analyzed for the final analysis (final datalock).

Follow-up population: The follow-up population is defined as patients who entered the follow-up period and completed the follow-up visit.

For the February 2021 DBL, adverse event (AE) Period 1 tables will be summarized by treatment in Period 1, which include treatment group of (PBO, BARI 1-mg, BARI-2mg, BARI 4-mg, Pooled BARI).

For final DBL, AE tables will be summarized by treatment in Period 2 as specified in [Table JAHN.6.1](#).

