6.4. Handling of Dropouts or Missing Data

Intercurrent events (ICH E9 R1) are events which occur after randomization such that subsequent data (collected after the intercurrent event) are difficult to interpret.

Depending on the estimand being addressed, different methods will be used to handle missing data as a result of intercurrent events. Intercurrent events can occur through the following:

- application of the censoring rule (including after permanent study drug discontinuation or for responders and partial responders [on Placebo or baricitinib 1-mg] who are rescued to a higher dose [baricitinib 2 mg or baricitinib 4 mg])
- retreatment after downtitration or early withdrawal
- discontinuation
- missing an intermediate visit prior to discontinuation or rescue
- lost to follow-up

Noncensor intercurrent events are events that are not due to the application of any censoring rule (ie, the last 3 items in the list above).

Note that as efficacy and health outcome data can accrue after a patient permanently discontinues study drug or is rescued to either baricitinib 2 mg or baricitinib 4 mg (for responders and partial responders on placebo or baricitinib 1 mg), a censoring rule will be applied to all efficacy and health outcome observations subsequent to these events depending on the estimand being addressed.

The *Period 1 censoring rule* will censor efficacy after permanent study drug discontinuation or for responders and partial responders (on placebo or baricitinib 1 mg) who are rescued to a higher dose (baricitinib 2 mg or baricitinib 4 mg). This censoring rule will be applied to all efficacy endpoints conducted for the responder, partial responder, and nonresponder mITT populations (defined in Section 6.2.1). For responders and partial responders, the censoring rule will censor efficacy data after permanent study drug discontinuation or rescue date, whichever occurs first. For nonresponders, the censoring rule will censor efficacy data after permanent study drug discontinuation.

The *Period 2 censoring rule* will censor efficacy data after permanent study drug discontinuation or after retreatment, whichever occurs first. This censoring rule will be applied to efficacy endpoints and safety conducted for the Period 2 population corresponding to the withdrawal and downtitration substudy.

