6.11. Efficacy Analyses

The general methods used to summarize efficacy data, including the definition of baseline value for assessments are described in Section 6.2.

Efficacy analyses will generally be analyzed according to the groups in Table JAHN.6.3 and patients will be analyzed according to the IP being analyzed in the objective.

Table JAHN.6.3. Efficacy Analyses: Comparisons or Treatment Paradigms

Treatment Period	Treatment Groups: Originating Study Treatment to JAHN Treatment	Comparison or Treatment Paradigms	Analysis
Treatment Period 1 (main JAHN protocol)	Responders and Partial Responders: PBO to PBO (PBO), BARI 1 mg to BARI 1 mg (BARI 1 mg), BARI 2 mg to BARI 2 mg (BARI 2 mg), BARI 4 mg to BARI 4 mg (BARI 4 mg)	PBO, BARI 1 mg, BARI 2 mg, BARI 4 mg; descriptive	Primary, Secondary, Exploratory
	Nonresponders: PBO to BARI 2 mg, PBO to BARI 4 mg, BARI 1 mg to BARI 2 mg, BARI 1 mg to BARI 4 mg, BARI 2 mg to BARI 2 mg, BARI 2 mg to BARI 4 mg, BARI 4 mg to BARI 4 mg	PBO to BARI 4 mg vs PBO to BARI 2 mg; BARI 1 mg to BARI 4 mg vs BARI 1 mg to BARI 2 mg; BARI 2 mg to BARI 4 mg vs BARI 2 mg to BARI 2 mg	Secondary, Exploratory
Treatment Period 2 (Randomized Withdrawal and Downtitration SubStudy)	Treatment Groups: Bari 4 mg at Week 52 Bari 4 mg to Bari 2 mg Bari 4 mg to PBO Bari 2 mg at Week 52	Bari 4 mg to Bari 2 mg Bari 4 mg to PBO	Secondary

Treatment Period	Treatment Groups: Originating Study Treatment to JAHN Treatment	Comparison or Treatment Paradigms	Analysis
	Bari 2 mg to Bari 1 mg Bari 2 mg to PBO	Bari 2 mg to Bari 1 mg Bari 2 mg to PBO	
Treatment Period 2 (Non substudy) (main JAHN population)	Treatment Groups: Bari 4 mg Bari 2 mg Bari 1 mg PBO	No comparison	Secondary, Exploratory
Treatment Period 2 (Non substudy) (open label Bari 2mg population)	Treatment Groups: Bari 2mg	No comparison	Secondary, Exploratory

Abbreviations: BARI = baricitinib; PBO = placebo.

[Table JAHN.6.4](#) includes the descriptions and derivations of the primary, secondary, and exploratory efficacy outcomes.

[Table JAHN.6.5](#) provides the detailed analyses including analysis type, method and imputation, population, time point, and comparisons for efficacy analyses.

Table JAHN.6.4. Description and Derivation of Primary, Secondary, and Exploratory Efficacy Outcomes

Measure	Description	Variable	Derivation / Comment	Imputation Approach if Missing Components

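### In the JAHN-alone AE and exposure tables, Table JAHN.6.1 has no by-dose row for time after retreatment or rescue, and no Period 2 AE row for placebo or 1-mg patients outside the substudy

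*SAP*

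**What the plan says.** SAP Section 6.2.1 analyses safety by the groups in Table JAHN.6.1 and sends the final-lock AE tables to its Period 2 rows. There are eight such rows: six substudy arms, plus non-substudy 2 mg and 4 mg.

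- The withdrawal and down-titration arms entered on 2 mg are "followed to end of study or censored at retreatment with BARI 2 mg"; those entered on 4 mg have the same wording with 4 mg. The stay-on-dose arms have no such limit: "Randomized to stay on BARI 2 mg in Treatment Period 2 followed to end of study".
- In Period 1 the placebo row reads "Placebo at entry to Study JAHN followed to end of Treatment Period 1 or censored at treatment change". The switch rows are tied to study entry, for example "PBO/BARI 1 mg switching to BARI 2 mg at entry to Study JAHN".
- Section 6.4 foresees rescue of "responders and partial responders [on Placebo or baricitinib 1-mg] who are rescued to a higher dose [baricitinib 2 mg or baricitinib 4 mg". On the Period 2 rule, which censors at discontinuation or retreatment, it says "This censoring rule will be applied to efficacy endpoints and safety conducted for the Period 2 population" corresponding to the substudy.
- Section 6.14 counts events only up to a dose or treatment change, and Section 6.14.1 ends exposure at the same point.
- Table JAHN.6.3 lists the Period 2 non-substudy efficacy groups of the main study as "Treatment Groups: Bari 4 mg Bari 2 mg Bari 1 mg PBO".
- Section 6.2.1 adds one pooled set for the final analysis: "An all-baricitinib exposure, defined as patients valid for the safety population with at least 1 dose of baricitinib anytime during Study JAHN".

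**The concern.** A safety table should place every patient-day of the safety population in some group. Here the censoring rules end a patient's time in one row, and for several groups no other row begins. The Period 2 safety population takes in anyone dosed in that period, so the patients concerned belong to the analysis but have no column. At stake is whether the study's own tables give the full by-dose exposure and event counts for 2 mg and 4 mg, and whether placebo and 1-mg patients outside the substudy are reported by group at all after Week 52.

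**Working it through.** The plan states no figure that can be reproduced for this point. The check sets each kind of patient-time against the rows of Table JAHN.6.1 and the windows in Sections 6.14 and 6.14.1.

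| Patient-time | By-dose AE and exposure row | Other cover |
|---|---|---|
| Withdrawal and down-titration arms, before retreatment | own arm | not needed |
| Same arms, after retreatment with 2 mg or 4 mg | none | all-baricitinib set; listings |
| 2-to-2 mg and 4-to-4 mg arms, after retreatment | own arm by Table JAHN.6.1; censored by Section 6.4 | documents disagree |
| Placebo or 1 mg rescued in Period 1, rest of Period 1 | none | all-baricitinib set; listings |
| 1 mg outside the substudy, Period 2 | none | all-baricitinib set; listings; box plots to Week 104 |
| Placebo outside the substudy, Period 2 | none | listings; box plots to Week 104 |
| Placebo or 1 mg rescued in Period 2 | none (the non-substudy 2-mg and 4-mg rows are for patients who stayed on that dose) | all-baricitinib set; listings |

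The placebo and 1-mg patients do exist in Period 2. Section 5.2 defines rerandomization only for patients on 2 mg or 4 mg, and Section 5.1 keeps everyone else on current treatment. Table JAHN.6.1 does carry placebo and 1-mg rows that run past Week 52, but it marks them for box plots only.

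The listings in Section 6.14 cover SAEs, deaths and AEs leading to discontinuation. A non-serious AE that does not lead to discontinuation, in a placebo patient outside the substudy in Period 2, therefore appears in no planned AE table or listing.

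**Scale of the retreatment gap**

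Inputs from the documents: about 600 substudy patients (SAP 6.1); 1:1:1 allocation, so 2 of 3 arms are censored at retreatment (SAP 5.2); Period 2 from Week 52 to Week 200, which is 148 weeks (SAP 5.1).

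- Patients in arms censored at retreatment: 600 × 2/3 = 400.
- From the addendum: 250 × 0.80 × 0.30 = 60, which reproduces the planned 60 (protocol 4.4 and 4.8.1); 60 × 2/3 = 40.

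Assumed, because the documents give neither: share retreated r = 20% to 60%; retreatment at t = 8 to 32 weeks after Week 52.

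- Patients affected: 400 × 0.20 = 80, up to 400 × 0.60 = 240.
- Patient-years with no dose row to Week 200: 400 × r × (148 − t) × 7/365.25. Low end: 80 × 116 × 7/365.25 = 178. High end: 240 × 140 × 7/365.25 = 644.
- To Week 104, with 52 in place of 148: 80 × 20 × 7/365.25 = 31, up to 240 × 44 × 7/365.25 = 202.
- Addendum patients affected: 40 × 0.20 = 8, up to 40 × 0.60 = 24, out of 250.

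For any given r and t the patient-years are upper values, since no later dropout is allowed for.

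**The case against.** The best defence is that censoring at a dose change is sound: it keeps the randomized arms clean. Retreated patients are selected on relapse, carry earlier exposure and have no concurrent comparator, so a pooled set plus listings is a defensible report. Section 6.14 also says that the fuller safety assessment is made in combined data, and leaves the other detailed assessments to an integrated safety plan. All of this stands as an argument for censoring the arms and against comparing retreated patients with anyone. It does not argue against a descriptive row that starts where the arm stops.

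Several stronger readings are tempting, and the documents do not support them:

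- *The events vanish from the report.* Mostly they do not. Listings keep the serious ones, and the all-baricitinib set keeps those on baricitinib.
- *The 2-mg and 4-mg safety record of the whole programme is understated.* Only the JAHN-alone tables can be judged. The integrated plan may assign this time by dose.
- *The missing placebo and 1-mg rows add to that understatement.* They cannot, because that time is not on 2 mg or 4 mg.
- *Everything after a Period 1 rescue is ungrouped.* A patient on 2 mg or 4 mg at Week 52 can enter a Period 2 row. For that patient only the rest of Period 1 is missing. Few placebo responders are expected in any case (SAP 6.2.3).
- *The addendum's aim of enlarging the 2-mg safety base is defeated.* Its patients have 52 weeks on open-label 2 mg, their data are pooled with the 2-mg group, and those outside the substudy are named in the Period 2 2-mg row. About 40 of 250 are in arms that can be censored this way.
- *Each affected patient loses about 148 weeks.* That is a ceiling. The SAP's revision history describes phased site closure, so many patients need not reach Week 200.

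**Conclusion.** The gap is real within the JAHN-alone by-dose AE and exposure tables. Following the stated rules leaves out time after retreatment in four arms, time after rescue in Period 1, and all Period 2 time of placebo and 1-mg patients outside the substudy. What is understated in these tables is total by-dose exposure and event counts; nothing here shows that rates within the existing rows are biased.

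About 400 of 600 planned substudy patients, about 40 of them from the addendum, are in arms censored at retreatment. How many are actually censored depends on a retreatment rate that the documents do not give, so the 80 to 240 patients and 178 to 644 patient-years are illustrations only. The size of the rescue gap and of the placebo and 1-mg gap cannot be derived from the documents.

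The contradiction on the stay-on-dose arms is separate and certain. If Section 6.4 is read literally, the post-retreatment gap extends to all six substudy arms. This is a change that should be made, since it is cheap and the cover elsewhere is only partial.

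**What to change.** Add these rows to Table JAHN.6.1, for the AE and exposure tables:

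- Period 2: Retreated BARI 2 mg and Retreated BARI 4 mg, each from first retreatment dose to end of study.
- Period 2: non-substudy PBO and non-substudy BARI 1 mg, censored at dose or treatment change.
- A post-rescue row by dose (2 mg, 4 mg), from first dose after rescue. State how a patient rescued in Period 1 passes to a Period 2 row at Week 52, so that no time is counted twice.

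Report AEs, SAEs and patient-years for each. Label the rows as non-randomized and make no comparison. Leave the censoring of the withdrawal and down-titration arms as it is.

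Reconcile Table JAHN.6.1 with Section 6.4 on whether safety data in the 2-to-2 mg and 4-to-4 mg arms are censored at retreatment. If they are, the retreated rows must take up that time too.

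The cost is extra columns from data already collected. The downside is that some groups will be small.

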### **4.8. Statistical Considerations**

#### **4.8.1. Sample Size Determination**

This addendum will aim to enroll approximately 250 additional patients  $\geq 18$  years of age into the JAHN Study. It is anticipated that approximately 80% of enrolled patients will complete the first 52 weeks (treatment period 1). Of those, it is expected 30% will enroll into the JAHN randomized withdrawal and down-titration substudy. This addendum is descriptive in nature and the sample size is not based on any statistical power calculations.

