6.14.3. Clinical Laboratory Evaluation

For the categorical laboratory analyses (shift and treatment emergent), the analysis period is defined as the treatment period plus up to 30 days off-drug follow-up time. The analysis period for the continuous laboratory analyses (eg, change from baseline by time point) is defined as the treatment period excluding off-drug follow-up time.

All laboratory tests will be presented using the International System (SI) and US conventional (CN) units. The performing central laboratory reference ranges will be used to define the low and high limits.

There is one special circumstance for laboratory values to be derived based on regularly scheduled, protocol-specified analytes. The low-density lipoprotein/high-density lipoprotein (LDL/HDL) ratio will be derived as the ratio of LDL cholesterol to HDL cholesterol. There are no central lab reference ranges for the LDL/HDL ratio.

The following will be conducted for the laboratory analytes collected quantitatively:

- **Box plots:** Values at each visit (starting at first visit in Study JAHN) and change from last baseline to each visit and to last postbaseline measure will be displayed in box plots for patients who have both a baseline and at least 1 postbaseline visit. The last nonmissing observation in the treatment period will be used as the last observation. Box plots will be provided for Treatment Period 1 and for Treatment Periods 1 and 2 combined. Individual measurements outside of reference limits will also be displayed using distinct symbols overlaying the box plot. Original-scale data will be used for the display but for some analytes (eg, immunoglobulins) a logarithmic scale may be used to aid in viewing the measures of central tendency and dispersion. Unplanned measurements will be excluded. Descriptive summary statistics will be included below the box plot along with p-values resulting from between-treatment comparison in change from last baseline to last observation. An ANCOVA model with explanatory term for treatment and the baseline value as a covariate will be used. These box plots will be used to evaluate trends over time and to assess a potential impact of outliers on central tendency summaries.

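### The combined Period 1 and 2 box-plot panel has no group for patients who stopped 2 mg or 4 mg before Week 52, while placebo and 1 mg keep their early stoppers

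*SAP*

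**What the plan says.** SAP Section 6.2.1, Table JAHN.6.1, has a separate block of groups for Treatment Periods 1 and 2 together, used only for box plots.

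- **Placebo:** "Placebo at entry to Study JAHN followed to end of study or censored at treatment change".
- **1 mg:** "BARI 1 mg followed to end of study or censored at dose or treatment change".
- **Six substudy groups:** each is defined by rerandomization at Week 52, for example "BARI 2 mg in Treatment Period 1, rerandomized to stay on BARI 2 mg in Treatment Period 2 followed to end of study".
- **Two non-substudy groups:** the 2-mg row takes patients who "did not enter the substudy and stayed on BARI 2 mg in Treatment Period 2 followed to end of study" and states that it includes the open-label addendum patients. The 4-mg row has the same form.

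The Period 1 block of the same table is different. Its 2-mg row reads "BARI 2 mg followed to end of Treatment Period 1 or censored at dose or treatment change", with no Period 2 condition.

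Three other rules bear on who should appear:

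- The safety population (Section 6.2.1) needs one dose in Study JAHN and no loss to follow-up at the first postbaseline visit.
- Section 6.14.3 admits to the box plots any patient with a baseline and at least one postbaseline visit. It plans one set for Period 1 and one for both periods, and places under the plots "p-values resulting from between-treatment comparison in change from last baseline to last observation", from an ANCOVA.
- Section 6.14.4 applies the same analyses to vital signs.

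**The concern.** A patient who took 2 mg or 4 mg and stopped at, say, Week 20 was neither rerandomized nor kept on the dose in Period 2, so none of the eight active-dose rows fits. A patient who stopped placebo or 1 mg at Week 20 stays in the placebo or 1-mg row. The combined panel thus conditions the two higher doses on reaching Period 2 and leaves the other two groups unconditioned.

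The selection works on a variable observed after treatment starts. Some early stoppers may have stopped because of a laboratory or vital-sign change. If so, the combined plots and their last-observation p-values would draw 2 mg and 4 mg from patients in whom that change was less common, without saying so. At an early visit such as Week 4, the Period 1 plot and the combined plot would also describe different sets of 2-mg and 4-mg patients, with no note to explain the difference.

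**Working it through.** **Step 1. Membership conditions, combined block of Table JAHN.6.1**

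| Groups | Number | Period 2 status required |
|---|---|---|
| Placebo, 1 mg | 2 | 0 of 2 |
| 2 mg or 4 mg, substudy | 6 | 6 of 6 (rerandomized) |
| 2 mg or 4 mg, non-substudy | 2 | 2 of 2 (stayed on dose) |

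So 8 of 8 active-dose groups at 2 mg or 4 mg carry the condition, and neither of the others does. The safety population and the box-plot inclusion rule carry none.

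**Step 2. The plan's own figure.** Protocol Section 4.8.1 gives about 250 addendum patients, about 80% completing 52 weeks, and 30% of those entering the substudy.

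- 250 × 0.80 = 200 completers
- 200 × 0.30 = 60 in the substudy, matching the 60 stated in Protocol Section 4.4
- 200 − 60 = 140 non-substudy continuers

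**Step 3. Patients without a group (addendum).** 250 × (1 − 0.80) = 50, or 20%. This is an upper figure: patients lost to follow-up at the first postbaseline visit, or with no postbaseline value, are outside the display anyway. It also treats completing 52 weeks as equivalent to entering Period 2.

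**Step 4. Possible shift in a dose's mean.** Let *d* be the share who stop before Week 52, and let stoppers and continuers have mean changes *m*s and *m*c. The mean over all patients is (1 − *d*)·*m*c + *d*·*m*s. With continuers only it is *m*c. The difference is *d*·(*m*s − *m*c).

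The documents give neither *d* for the main-protocol arms nor *m*s − *m*c for any analyte. The following values are assumptions:

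| Dropout *d* | Gap 0.25 SD | Gap 0.5 SD | Gap 1.0 SD |
|---|---|---|---|
| 10% | 0.025 | 0.05 | 0.10 |
| 20% | 0.05 | 0.10 | 0.20 |
| 30% | 0.075 | 0.15 | 0.30 |

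These shifts refer to a dose taken as a whole. The panel splits each dose into four rows, so no single row carries exactly this number.

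**The case against.** The strongest reply is that the early stoppers are shown elsewhere. Section 6.14.3 plans Period 1 box plots with the same ANCOVA, and Period 1 high/low tables that include unplanned measurements and up to 30 days off drug. The Period 1 groups keep everyone. Adverse events leading to discontinuation are also tabulated for Period 1 and listed for both periods. This stands. A reader might infer that early stoppers drop out of the laboratory and vital-sign evaluation altogether, or that a drug effect is concealed. The documents do not support that: the gap is confined to the combined display.

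Second, the panel may not be produced. Section 6.14 limits the February 2021 and final locks to disposition and adverse-event tables and sends other safety work to an integrated plan. The panel heading still says Week 0-104 although Period 2 now runs to Week 200, which suggests carried-over text. This is a fair doubt, but Sections 6.2.2, 6.14 and 6.14.3 still plan the combined plots.

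Third, placebo and 1 mg are not an unselected comparator. Under Sections 5.2 and 6.11, patients who remain on them are responders and partial responders only, and they are censored at treatment change. The comparison was never like for like. That limits how much any p-value here can mean, but does not justify a further, unstated selection on one side.

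Fourth, a reader might attach a definite percentage understatement to the panel. The documents supply no means for stoppers and continuers, so neither the direction nor the size of the shift can be fixed.

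The sentence in Section 6.2.1 on analysing patients by assigned regimen does not close the gap, because the row definitions themselves require the patient to have stayed on the dose in Period 2.

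**Conclusion.** The point holds for the combined Period 1 and 2 panel and its p-values, for laboratory analytes and vital signs. It is a stated rule that selects one way for 2 mg and 4 mg and another for placebo and 1 mg, and it conflicts with the SAP's own population and inclusion rules.

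The size in patients is up to about 50 of 250 in the addendum, resting on the protocol's 80% completion assumption; the number in the main-protocol arms is unknown. The effect on a mean is unknown too. The 0.025-0.30 SD range rests entirely on the assumed dropout and gap. No efficacy endpoint is affected, and the Period 1 safety displays are intact. The correction is worth making if the panel will be run; otherwise the text should go.

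**What to change.** Choose one of three.

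1. **Split at Week 52 (preferred).** Show Weeks 0-52 by Period 1 treatment group for all safety-population patients, and only Weeks 52 onward by Period 2 group, with p-values computed within each part. The Period 2 block of Table JAHN.6.1 has no placebo or 1-mg row, so rows for patients continuing on those would have to be added.
2. **Keep the combined groups.** Apply the same Period 2-entry condition to placebo and 1 mg, and label the panel as restricted to patients entering Period 2.
3. **If the panel is not produced at the final lock,** delete it from Table JAHN.6.1 and from Sections 6.2.2, 6.14 and 6.14.3.

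Adding early stoppers to the two non-substudy rows alone would not be enough. Six of the eight active groups would still contain only patients who reached Week 52. In the addendum the non-substudy row would mix 50 stoppers with 140 continuers (50/190 = 26% stoppers).

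The cost is a few table rows and one display rerun, with no new data. The second option also leaves fewer placebo and 1-mg patients in the panel.
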